5.3. Lifestyle Considerations

Throughout the study, participants may undergo medical assessments and review of compliance with requirements before continuing in the study.

5.3.1. Meals and Dietary Restrictions

During the confinement period, participants will consume only food and beverages that are provided to them by the CRU staff. Standard meals (e.g., breakfast, lunch, dinner, and snack) will be provided to the participants while resident at the CRU.

Dabigatran and selpercatinib will be administered with food using a standardized unit meal.

The macronutrient composition of the standardized meals for dabigatran and selpercatinib administration should be targeted to provide approximately 50% of the calories from carbohydrates, 15% protein, and 35% fat. The total calories for the standardized meal to be consumed with each dose is expected to be approximately 685 calories. Subjects will be encouraged to eat the entire meal.

Each component of the meal will be weighed separately and documented in grams pre and post meal to determine the percentage of the meal consumed in grams by the subject. The nutritional intake will be documented in grams and recorded in the electronic case report form (eCRF).

Participants will complete the standardized meal 30 minutes prior to administration of study intervention and participants should eat this meal in 30 minutes or less. No additional food should be allowed for at least 4 hours after drug administration.

5.3.2. Caffeine, Alcohol, and Tobacco

Participants will abstain from ingesting caffeine- or xanthine-containing products (e.g., coffee, tea, cola drinks, and chocolate) for 48 hours prior to admission until after discharge from the CRU

Participants will abstain from alcohol for 48 prior to admission until after discharge from the CRU.

Participants who use tobacco products will be instructed that use of nicotine-containing products (including nicotine patches) will not be permitted while they are in the clinical unit.

5.3.3. Activity

Participants will abstain from strenuous exercise for 48 hours before each blood collection for clinical laboratory tests. Participants may participate in light recreational activities during the study (e.g., watching television, reading).

5.4. Screen Failures

Screen failures are defined as participants who consent to participate in the clinical study but are not subsequently assigned to study intervention.

Individuals who do not meet the criteria for participation in this study (screen failure) may not be rescreened. Repeating of laboratory tests during the screening period or repeating screening tests to comply with the protocol designated screening period does not constitute rescreening.

6. Study Intervention

Study intervention is defined as any investigational intervention(s), marketed product(s), placebo, or medical device(s) intended to be administered to/used by a study participant according to the study protocol.

6.1. Study Interventions Administered

Table JZJV.1. Study Interventions Administered

Study Intervention	Selpercatinib	Dabigatran etexilate
Dosage Formulation	Capsule	Capsule
Unit dose strength(s)/Dosage Level(s)	2 × 80-mg capsules (160 mg selpercatinib)	150-mg capsule
Route of Administration	Oral	Oral
Dosing Instructions	2 capsules taken on Day 8	1 capsule taken on Day 1 and 1 capsule taken on Day 8

6.1.1. Administration Details

A single oral dose of dabigatran etexilate 150 mg will be administered in the morning of Day 1 with approximately 240 mL of room temperature water while in a sitting position. On the morning of Day 8, a single dose of dabigatran etexilate 150 mg and selpercatinib 160 mg will be administered orally with approximately 240 mL of room temperature water while in a sitting position. Participants will not be allowed to lie supine for 2 hours after dosing, unless clinically indicated or for study procedures.

Dabigatran etexilate and selpercatinib capsules should be swallowed whole. Participants should not break, crush, chew, or empty the contents of either capsule.

On dosing days, participants will adhere to meal restrictions as outlined in Section [5.3.1](#).

6.2. Preparation/Handling/Storage/Accountability

1. The investigator or designee must confirm appropriate temperature conditions have been maintained during transit for all study intervention received and any discrepancies are reported and resolved before use of the study intervention.
2. Only participants enrolled in the study may receive study intervention and only authorized site staff may supply or administer study intervention. All study intervention must be stored in a secure, environmentally controlled, and monitored (manual or automated) area in accordance with the labeled storage conditions with access limited to the investigator and authorized site staff.

3. The investigator, institution, or the head of the medical institution (where applicable) is responsible for study intervention accountability, reconciliation, and record maintenance (i.e., receipt, reconciliation, and final disposition records).
4. The investigator or designee will return all unused study interventions to Lilly or its designee at the end of the study. In some cases, sites may destroy the material if, during the CRU selection, the evaluator has verified and documented that the site has appropriate facilities and written procedures to dispose of clinical materials.

6.3. Measures to Minimize Bias: Randomization and Blinding

This is an open-label study. There is no bias as the primary endpoint is PK and objective in measure.

6.4. Study Intervention Compliance

Participants are dosed at the site and will receive study intervention directly from the investigator or designee, under medical supervision. The date and time of each dose administered in the clinic will be recorded in the source documents and recorded in the eCRF. The dose of study intervention and study participant identification will be confirmed at the time of dosing by a member of the study site staff other than the person administering the study intervention. Study site personnel will examine each participant's mouth to ensure that the study intervention was ingested.

6.5. Concomitant Therapy

Any medication or vaccine (including over-the-counter or prescription medicines, vitamins, and/or herbal supplements) that the participant is receiving at the time of enrollment or receives during the study must be recorded along with:

- Reason for use
- Dates of administration including start and end dates
- Dosage information including dose and frequency for concomitant therapy of special interest

The medical monitor should be contacted if there are any questions regarding concomitant or prior therapy.

Participants must abstain from taking prescription or nonprescription drugs (including vitamins and dietary or herbal supplements) within 14 days before the start of study intervention until discharge from the study.

Acetaminophen, at doses of \leq 2 grams/24 hours, is permitted for use at the discretion of the investigator for the treatment of headache, etc. Contraceptive medication is permitted as per the contraception requirements (Appendix 10.4), and hormone replacement therapy is also allowed.

Other medication may be considered on a case-by-case basis by the investigator in consultation with the Lilly clinical pharmacologist (CP)/clinical research physician (CRP), or designee.

6.6. Dose Modification

Dose modification is not permitted in this study.

6.7. Intervention after the End of the Study

Not applicable.

7. Discontinuation of Study Intervention and Participant Discontinuation/Withdrawal

[figure not shown]
Participants discontinuing from the study prematurely for any reason must complete and follow-up procedures per Section 1.3 of this protocol.

7.1. Discontinuation of Study Intervention

In rare instances, it may be necessary for a participant to permanently discontinue (definitive discontinuation) study intervention. If study intervention is definitively discontinued, the participant will remain in the study to be evaluated for safety. See the SoA for data to be collected at the time of discontinuation of study intervention and follow-up and for any further evaluations that need to be completed.

Study intervention will be discontinued **for a participant** if liver chemistry stopping criteria are met.

Phase 1 Liver Chemistry Stopping Algorithm

Abbreviations: ALT = alanine transaminase; INR = international normalized ratio; SAE = serious adverse event; ULN = upper limit of normal.

Liver Safety: Suggested Actions and Follow-up Assessments can be found in Appendix 10.6.

A participant who meets either bulleted criterion following single ECG assessment should have ECG repeated. If the participant still meets either bulleted criterion they will be withdrawn from the study.

- QTc, QTcB, QTcF >500 msec
- Change from baseline: QTc >60 msec

If a clinically significant finding is identified (including, but not limited to changes from baseline in QTc using Bazett's formula or QTcF) after enrollment, the investigator or qualified designee will determine if the participant can continue in the study and if any change in participant management is needed. This review of the ECG printed at the time of collection must be documented. Any new clinically relevant finding should be reported as an AE.

See the SoA for data to be collected at the time of intervention discontinuation and follow-up and for any further evaluations that need to be completed.

7.2. Participant Discontinuation/Withdrawal from the Study

A participant may withdraw from the study:

- at any time at his/her own request
- at the request of his/her designee (for example, parents or legal guardian)
- at the discretion of the investigator for safety, behavioral, compliance, or administrative reasons
- if the participant becomes pregnant during the study
- if enrollment in any other clinical study involving an investigational product or enrollment in any other type of medical research judged not to be scientifically or medically compatible with this study

Discontinuation is expected to be uncommon.

At the time of discontinuing from the study, if possible, an early discontinuation visit should be conducted, as shown in the SoA. See the SoA for data to be collected at the time of study discontinuation and follow-up and for any further evaluations that need to be completed. The participant will be permanently discontinued both from the study intervention and from the study at that time.

If the participant withdraws consent for disclosure of future information, the sponsor may retain and continue to use any data collected before such a withdrawal of consent. If a participant withdraws from the study, he/she may request destruction of any samples taken and not tested, and the investigator must document this in the site study records.

7.2.1. Discontinuation of Inadvertently Enrolled Participants

If the sponsor or investigator identify a participant who did not meet enrollment criteria and was inadvertently enrolled, then the participant should be discontinued from study treatment unless there are extenuating circumstances that make it medically necessary for the participant to continue on study treatment. If the investigator and the sponsor CRP agree it is medically appropriate to continue, the investigator must obtain documented approval from the sponsor CRP to allow the inadvertently enrolled participant to continue in the study with or without treatment with investigational product. Safety follow-up is as outlined in Section 1.3 (Schedule of

Activities), Section 8.2 (Safety Assessments), and Section 8.3 (Adverse Events and Serious Adverse Events) of the protocol.

7.3. Lost to Follow-up

A participant will be considered lost to follow-up if he or she repeatedly fails to return for scheduled visits and is unable to be contacted by the study site. Site personnel are expected to make diligent attempts to contact participants who fail to return for a scheduled visit or were otherwise unable to be followed up by the site.

Discontinuation of specific sites or of the study as a whole are handled as part of Appendix 10.1.

8. Study Assessments and Procedures

- Study procedures and their timing are summarized in the SoA. Protocol waivers or exemptions are not allowed.
- Immediate safety concerns should be discussed with the sponsor immediately upon occurrence or awareness to determine if the participant should continue or discontinue study intervention.
- Adherence to the study design requirements, including those specified in the SoA, is essential and required for study conduct.
- All screening evaluations must be completed and reviewed to confirm that potential participants meet all eligibility criteria. The investigator will maintain a screening log to record details of all participants screened and to confirm eligibility or record reasons for screening failure, as applicable.

8.1. Efficacy Assessments

Not applicable.

8.2. Safety Assessments

8.2.1. Physical Examinations

- Physical examinations should be conducted according to the SoA (Section 1.3).
- A full physical examination will include, at a minimum, assessments of the cardiovascular, respiratory, gastrointestinal, and neurological systems. Height and weight will also be measured and recorded.
- Investigators should pay special attention to clinical signs related to previous serious illnesses.

8.2.2. Vital Signs

- For each participant, vital signs measurements should be conducted according to the SoA (Section 1.3).
- Blood pressure and pulse rate should be measured singly after at least 5 minutes supine. For each individual participant, the same cuff size should be used throughout the study for the measurements of blood pressure. The cuff should be attached to the participant's dominant arm.
- Unscheduled orthostatic vital signs should be assessed, if possible, during any AE of dizziness or posture-induced symptoms. Where orthostatic measurements are required, participants should be supine for at least 5 minutes and then participants will stand, and standing blood pressure will be measured after 2 minutes, but no longer than 3 minutes. If

the participant feels unable to stand, supine vital signs only will be collected. Additional vital signs may be measured if warranted.

8.2.3. Electrocardiograms

- For each participant, single 12-lead ECGs will be obtained as outlined in the SoA (see Section 1.3). Refer to Section 7 for QTc withdrawal criteria and any additional QTc readings that may be necessary.
- Electrocardiograms must be recorded before collecting any blood samples. Participants must be supine for approximately 5 to 10 minutes before ECG collection and remain supine but awake during ECG collection. Electrocardiograms may be obtained at additional times, when deemed clinically necessary. All ECGs recorded should be stored at the investigational site.
- Electrocardiograms will be interpreted by the investigator at the site as soon after the time of ECG collection as possible, and ideally while the participant is still present, to determine whether the participant meets entry criteria at the relevant visit(s) and for immediate participant management, should any clinically relevant findings be identified.
- If a clinically significant finding is identified (including, but not limited to, changes in QT/QTc interval from baseline) after enrollment, the investigator will determine if the participant can continue in the study. The investigator, or qualified designee, is responsible for determining if any change in participant management is needed and must document his/her review of the ECG printed at the time of collection. Any new clinically relevant finding should be reported as an AE.

8.2.4. Clinical Safety Laboratory Assessments

- See Appendix 10.2 for the list of clinical laboratory tests to be performed and to the SoA for the timing and frequency.
- The investigator must review the laboratory report, document this review, and record any clinically relevant changes occurring during the study in the AE section of the eCRF. The laboratory reports must be filed with the source documents.
- All laboratory tests with values considered clinically significantly abnormal during participation in the study after the last dose of study intervention should be repeated until the values return to normal or baseline or are no longer considered clinically significant by the investigator or medical monitor.
 - If such values do not return to normal/baseline within a period of time judged reasonable by the investigator, the etiology should be identified, and the sponsor notified.
 - All protocol-required laboratory assessments, as defined in Appendix 10.2, must be conducted in accordance with the laboratory manual and the SoA.

- If laboratory values from non-protocol specified laboratory assessments performed at the institution's local laboratory require a change in participant management or are considered clinically significant by the investigator (e.g., SAE or AE), then the results must be recorded in the eCRF.

8.2.5. Safety Monitoring

The Lilly CP or CRP/scientist will monitor safety data throughout the course of the study.

Lilly will review SAEs within time frames mandated by company procedures. The Lilly CP or CRP will periodically review the following data:

- trends in safety data
- laboratory analytes including hematology and chemistry

When appropriate, the Lilly CP or CRP will consult with the functionally independent Global Patient Safety therapeutic area physician or clinical research scientist.

8.2.5.1. Hepatic Safety

Close hepatic monitoring

Laboratory tests (Appendix 10.6), including ALT, AST, ALP, TBL, direct bilirubin, gamma-glutamyl transferase, and creatine kinase, should be repeated within 48 to 72 hours to confirm the abnormality and to determine if it is increasing or decreasing, if one or more of these conditions occur:

If a participant with baseline results of ...	develops the following elevations:
ALT or AST $<1.5 \times$ ULN	ALT or AST $\geq 3 \times$ ULN
ALP $<1.5 \times$ ULN	ALP $\geq 2 \times$ ULN
TBL $<1.5 \times$ ULN	TBL $\geq 2 \times$ ULN (except for patients with Gilbert's syndrome)
ALT or AST $\geq 1.5 \times$ ULN	ALT or AST $\geq 2 \times$ baseline
ALP $\geq 1.5 \times$ ULN	ALP $\geq 2 \times$ baseline
TBL $\geq 1.5 \times$ ULN	TBL $\geq 2 \times$ baseline (except for patients with Gilbert's syndrome)

If the abnormality persists or worsens, clinical and laboratory monitoring and evaluation for possible causes of abnormal liver tests should be initiated by the investigator in consultation with the Lilly-designated medical monitor. At a minimum, this evaluation should include physical examination and a thorough medical history, including symptoms, recent illnesses (for example, heart failure, systemic infection, hypotension, or seizures), recent travel, history of concomitant medications (including over-the-counter), herbal and dietary supplements, history of alcohol drinking and other substance abuse.

Initially, monitoring of symptoms and hepatic biochemical tests should be done at a frequency of 1 to 3 times weekly, based on the participant's clinical condition and hepatic biochemical tests. Subsequently, the frequency of monitoring may be lowered to once every 1 to 2 weeks, if the

participant's clinical condition and laboratory results stabilize. Monitoring of ALT, AST, ALP, and TBL should continue until levels normalize or return to approximate baseline levels.

Comprehensive hepatic evaluation

A comprehensive evaluation should be performed to search for possible causes of liver injury if one or more of these conditions occur:

If a participant with baseline results of...	develops the following elevations:
ALT or AST $<1.5 \times$ ULN	ALT or AST $\geq 3 \times$ ULN with hepatic signs/symptoms*, or ALT or AST $\geq 5 \times$ ULN
ALP $<1.5 \times$ ULN	ALP $\geq 3 \times$ ULN
TBL $<1.5 \times$ ULN	TBL $\geq 2 \times$ ULN (except for patients with Gilbert's syndrome)
ALT or AST $\geq 1.5 \times$ ULN	ALT or AST $\geq 2 \times$ baseline with hepatic signs/symptoms*, or ALT or AST $\geq 3 \times$ baseline
ALP $\geq 1.5 \times$ ULN	ALP $\geq 2 \times$ baseline
TBL $\geq 1.5 \times$ ULN	TBL $\geq 1.5 \times$ baseline (except for patients with Gilbert's syndrome)

* Hepatic signs/symptoms are severe fatigue, nausea, vomiting, right upper quadrant abdominal pain, fever, rash, and/or eosinophilia $>5\%$.

At a minimum, this evaluation should include physical examination and a thorough medical history, as outlined above, as well as tests for prothrombin time/international normalized ratio; tests for viral hepatitis A, B, C, or E; tests for autoimmune hepatitis; and an abdominal imaging study (for example, ultrasound or computed tomography scan).

Based on the participant's history and initial results, further testing should be considered in consultation with the Lilly-designated medical monitor, including tests for hepatitis D virus, cytomegalovirus, Epstein-Barr virus, acetaminophen levels, acetaminophen protein adducts, urine toxicology screen, Wilson's disease, blood alcohol levels, urinary ethyl glucuronide, and serum phosphatidylethanol. Based on the circumstances and the investigator's assessment of the participant's clinical condition, the investigator should consider referring the participant for a hepatologist or gastroenterologist consultation, magnetic resonance cholangiopancreatography, endoscopic retrograde cholangiopancreatography, cardiac echocardiogram, or a liver biopsy.

Additional hepatic data collection (hepatic safety eCRF) in study participants who have abnormal liver tests during the study:

Additional hepatic safety data collection in hepatic safety eCRFs should be performed in study participants who meet 1 or more of the following 5 conditions:

1. Elevation of serum ALT to $\geq 5 \times$ ULN on 2 or more consecutive blood tests (if baseline ALT $<1.5 \times$ ULN)
 - In participants with baseline ALT $\geq 1.5 \times$ ULN, the threshold is ALT $\geq 3 \times$ baseline on 2 or more consecutive tests
2. Elevated TBL to $\geq 2 \times$ ULN (if baseline TBL $<1.5 \times$ ULN) (except for cases of known Gilbert's syndrome)

- In participants with baseline TBL $\geq 1.5 \times$ ULN, the threshold should be TBL $\geq 2 \times$ baseline
- 3. Elevation of serum ALP to $\geq 2 \times$ ULN on 2 or more consecutive blood tests (if baseline ALP $< 1.5 \times$ ULN)
 - In participants with baseline ALP $\geq 1.5 \times$ ULN, the threshold is ALP $\geq 2 \times$ baseline on 2 or more consecutive blood tests
- 4. Hepatic event considered to be an SAE
- 5. Discontinuation of study drug due to a hepatic event

NOTE: the interval between the 2 consecutive blood tests should be at least 2 days.

8.3. Adverse Events and Serious Adverse Events

Product Complaints are covered in Section [8.3.6](#).

Adverse events will be reported by the participant (or, when appropriate, by a caregiver, surrogate, or the participant's legally authorized representative).

The investigator and any qualified designees are responsible for detecting, documenting, and recording events that meet the definition of an AE or SAE and remain responsible for following up AEs that are serious, considered related to the study intervention or study procedures, or that caused the participant to discontinue the study intervention (see Section [7](#)).

8.3.1. Time Period and Frequency for Collecting AE and SAE Information

All SAEs will be collected from the signing of the ICF until participation in the study has ended.

All AEs will be collected from the start of intervention until the follow-up visit.

Medical occurrences that begin before the start of study intervention but after signing of the ICF will be recorded on the Adverse Event eCRF.

Although all AEs after signing the ICF are recorded by the site in the eCRF/electronic data entry, SAE reporting to the sponsor begins after the participant has signed the ICF and has received study drug. However, if an SAE occurs after signing the ICF, but prior to receiving selpercatinib, it needs to be reported ONLY if it is considered reasonably possibly related to study procedures.

All SAEs will be recorded and reported to the sponsor or designee immediately and under no circumstance should this exceed 24 hours, as indicated in Appendix [10.3](#). The investigator will submit any updated SAE data to the sponsor within 24 hours of it being available.

Investigators are not obligated to actively seek AEs or SAEs after conclusion of the study participation. However, if the investigator learns of any SAE, including a death, at any time after a participant has been discharged from the study, and he/she considers the event to be reasonably related to the study intervention or study participation, the investigator must promptly notify the sponsor.

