2.3. Benefit/Risk Assessment

There is no anticipated therapeutic benefit for the participants in this study. However, participants may benefit from the screening procedures (through detection of unknown health issues) even if they receive no therapeutic benefit from the study.

The dose of selpercatinib to be given in this study is 160 mg, as it is the highest approved dose. The safety profile of selpercatinib is very well tolerated in healthy volunteers and is clinically manageable, with the low rates of study drug discontinuation due to AEs. As outlined in the IB, the most common toxicities associated with selpercatinib are monitorable and reversible and include dry mouth, diarrhea, hypertension, fatigue, constipation, AST/ALT elevation, headache, nausea, edema peripheral, abdominal pain, rash, electrocardiogram QT prolonged, cough, vomiting, dyspnea and increased blood creatinine. Events of special interest include hypersensitivity, liver-function test abnormalities, thrombocytopenia, and hypertension.

The dabigatran dose to be administered in this study (150 mg) is within the therapeutic range (see Section 4.3), and has previously been administered to healthy volunteers with no tolerability concerns in other DDI studies (e.g., I8D-MC-AZEE; NCT02568397).

More detailed information about the known and expected benefits and risks and reasonably expected AEs of selpercatinib may be found in the IB.

3. Objectives and Endpoints

Objectives	Endpoints
Primary	
• To evaluate the effect of selpercatinib on P-gp activity in healthy participants• C_{max} and $AUC(0-\infty)$ of dabigatran to assess P-gp activity
Secondary	
• To evaluate the safety and tolerability of dabigatran in combination with selpercatinib in healthy participants• To evaluate the pharmacokinetics of selpercatinib• Summary of the number of treatment-emergent adverse events and serious adverse events• C_{max}, $AUC(0-\infty)$, and t_{max} of selpercatinib

4. Study Design

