4.2. Scientific Rationale for Study Design

A single 160-mg dose of selpercatinib was selected as it is the highest approved dose for selpercatinib use in adults.

In order to allow each participant to act as his/her own control for safety and PK comparisons, a fixed sequence design has been selected. This study will also be open-label as the study primary endpoint PK measures are objective rather than subjective.

Based on the $t_{1/2}$ of dabigatran, a period of 7 days between dabigatran doses is considered sufficient time for the study drug to washout.

Conducting the study in healthy participants mitigates the potential confounding effects of the disease state and concomitant medications in participants with metastatic RET fusion-positive NSCLC, advanced or metastatic RET-mutant MTC, or advanced or metastatic RET fusion-positive thyroid cancer. A population of healthy participants is frequently used in the assessment of the PK of both small and large molecules.

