10.3.4. Reporting of SAEs**SAE Reporting via Paper CRF**

- Facsimile transmission of the SAE paper CRF is the preferred method to transmit this information to the medical monitor or the SAE coordinator.
- Initial notification via telephone does not replace the need for the investigator to complete and sign the SAE CRF pages within the designated reporting time frames.
- The investigator or site must alert the Lilly CRP/CP, or its designee, of any SAE as soon as practically possible.

Additionally, the investigator or site must alert Lilly Global Patient Safety, or its designee, of any SAE within 24 hours of investigator awareness of the event via a sponsor-approved method. If alerts are issued via telephone, they are to be immediately followed with official notification on study-specific SAE forms. This 24-hour notification requirement refers to the initial SAE information and all follow-up SAE information.

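### Protocol 8.3.1 lifts expedited SAE reporting until selpercatinib is given on Day 8, although dabigatran is given on Day 1; this contradicts its own all-SAEs rule and Section 10.3.4

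*Protocol*

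**What the plan says.** Protocol Section 8.3.1 contains three statements about when an SAE goes to the sponsor.

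- Start of reporting: "SAE reporting to the sponsor begins after the participant has signed the ICF and has received study drug".
- Exception, in the sentence that follows: an SAE after consent but "prior to receiving selpercatinib, it needs to be reported ONLY if it is considered reasonably possibly related to study procedures".
- General rule, in the next paragraph: "All SAEs will be recorded and reported to the sponsor or designee immediately and under no circumstance should this exceed 24 hours".

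Section 10.3.4 adds two alert duties, neither with an exception. The site must alert the sponsor's physician or pharmacologist "of any SAE as soon as practically possible", and the sponsor's global safety group "of any SAE within 24 hours of investigator awareness of the event".

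Section 6 defines study intervention to include marketed products given under the protocol. Table JZJV.1 in Section 6.1 lists both dabigatran etexilate (Days 1 and 8) and selpercatinib (Day 8 only).

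**The concern.** The exception is tied to the wrong event. It runs until selpercatinib is given, but by then every participant has already taken another study intervention, an anticoagulant, a week earlier. An SAE related to dabigatran and not to a procedure therefore falls inside the exception during the whole dabigatran-alone period.

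A site that follows the exception could delay or omit the expedited report of, for example, a bleed on Day 2. A site that follows the general rule or Section 10.3.4 would report it within 24 hours. Section 8.4 itself anticipates emergency bleeding caused by dabigatran, in the context of overdose. Section 8.3.4 describes prompt notification as essential to participant safety and to the sponsor's legal obligations.

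**Working it through.** No statistical figure is in dispute. The check is a comparison of the passages, followed by the length of the affected window.

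**1. The rules applied to one case.** Take an SAE on Day 3 that is judged related to dabigatran and unrelated to any procedure.

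| Rule | Must it be reported to the sponsor? |
|---|---|
| 8.3.1, exception before selpercatinib | No |
| 8.3.1, reporting starts on receipt of study drug | Yes, if study drug includes dabigatran |
| 8.3.1, all SAEs | Yes, within 24 hours |
| 10.3.4, alert to the sponsor's physician or pharmacologist | Yes, as soon as practicable |
| 10.3.4, alert to the global safety group | Yes, within 24 hours |

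**2. Can 'study procedures' be read to include dosing?** No. Section 8.3 makes the investigator responsible for following up AEs that are, among other categories, "considered related to the study intervention or study procedures". Intervention and procedure are separate categories there, and dabigatran is an intervention under Section 6 and Table JZJV.1.

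**3. Does 'study drug' mean selpercatinib only?** The protocol is not consistent. Section 4.2 uses the term for dabigatran: "a period of 7 days between dabigatran doses is considered sufficient time for the study drug to washout". Section 2.3 uses it for selpercatinib: "low rates of study drug discontinuation due to AEs". The conflict with the start-of-reporting sentence therefore depends on which meaning is taken. The conflicts with the all-SAEs rule and with Section 10.3.4 do not, because neither uses the term.

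**4. Length of the window, participant who receives both doses.** Inputs: dosing days from Table JZJV.1; follow-up 14 to 17 days after the final dose from Section 4.1.

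- Window: Day 8 − Day 1 = 7 days.
- Follow-up: Day 8 + 14 = Day 22, to Day 8 + 17 = Day 25.
- First dose to follow-up: 22 − 1 = 21 days, to 25 − 1 = 24 days.
- Share of that time: 7/24 = 29.2%, to 7/21 = 33.3%.

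**5. Participant dosed on Day 1 only.** Selpercatinib is never received, so read literally the exception does not lapse while participation continues. Section 7.1 keeps a participant who discontinues treatment in the study for safety evaluation. With Day 1 as the final dose, follow-up falls between Day 1 + 14 = Day 15 and Day 1 + 17 = Day 18. An early discontinuation visit under Section 7.2 would shorten this.

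**The case against.** The strongest reply is that selpercatinib is a one-word drafting slip. Read with the sentence before it, the exception most naturally means full reporting once dosing has begun and only procedure-related SAEs before that. On this view few sites would apply it after Day 1. The intent is plausible, but the text does not say it, and the remedy for a slip in an operative reporting rule is to correct it.

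A second reply is that a specific exception beside a general rule is not a contradiction, and that the 24-hour sentence and Section 10.3.4 only set timing for whatever is reportable. For the time before any dose, that reading works. After the Day 1 dabigatran dose it makes matters worse, because the exception would then prevail and the dabigatran event would properly go unreported.

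A third reply concerns weight, and most of it stands:

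- SAEs are collected from consent and recorded in the eCRF, and SAP Section 9.4.1 lists them.
- Section 8 calls for immediate safety concerns to be discussed with the sponsor, and Section 8.2.5 has the sponsor monitoring safety data throughout.
- Section 8.3.2 sends sites to Appendix 10.3 for transmitting SAE reports, and that appendix has no such exception.
- Under Section 4.1, participants who receive both doses are resident in the unit for the whole window.

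These routes make a missed report unlikely, but none of them replaces the formal 24-hour report.

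It is also fair to say that the text is silent on someone who never receives selpercatinib, so the Day 15 to Day 18 figure rests on the literal wording.

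**Conclusion.** The concern holds and should be fixed. For a dabigatran-related SAE between the Day 1 and Day 8 doses, the exception in Section 8.3.1 cannot be reconciled with the all-SAEs rule in the same section or with either alert rule in Section 10.3.4. It also conflicts with the sentence immediately before it if study drug has the meaning used in Section 4.2.

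The window is 7 days for each participant who goes on to Day 8, and at most until Day 15 to Day 18 for one who does not. These figures, and the 29% to 33% share, are upper bounds on calendar time and do not estimate how many reports would be lost. The exposure is confined to expedited reporting of a rare event. The SAE endpoint and the SAP summaries are not affected.

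**What to change.** The sponsor should reconcile Sections 8.3.1 and 10.3.4.

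1. In 8.3.1, replace the exception's reference to receipt of selpercatinib with *prior to the first dose of any study intervention (dabigatran etexilate or selpercatinib)*. In the preceding sentence, replace the reference to receipt of study drug with *has received the first dose of any study intervention*. This alone removes the Day 1 to Day 8 conflict.

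2. Optionally, link the remaining pre-dose exception to the general rules. After the all-SAEs sentence in 8.3.1, state that SAEs are recorded from consent; that those before the first dose of any study intervention and not related to procedures need not go to the sponsor; and that any reportable pre-dose SAE keeps the immediate/24-hour limit. In 10.3.4, add that 8.3.1 identifies which pre-dose SAEs are exempt and that the time limits apply to all others. This partly repeats text already in 8.3.1, so it clarifies but is not essential.

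The cost is two replaced phrases, a few short sentences if step 2 is taken up, a protocol amendment and site notification. No procedures, samples or data items are added.
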